Data analysis: The study cohorts will be followed from the start date for the first occurrence of any one of the study endpoints. A minimum lag time of 6 months will be assumed between the start of exposure and the occurrence of related study endpoints. Person-years of follow-up will be classified according to ever use, single use, and switching/multiple use of tacrolimus and pimecrolimus and to cumulative dose and duration of exposure. The main exposures of interest will be the cumulative dose of topical tacrolimus and pimecrolimus and time since first exposure.

The analysis will be conducted at two levels: a country-specific analysis conducted at each database research partner and an overall analysis conducted at the coordinating center. The approach is for each database research partner to create stratified tables with cross-classifications of patient and person-time counts by exposure category, endpoint, deciles of exposure propensity scores, age, sex, data source, and type of prescriber of first prescription when available. The coordinating center will estimate overall measures of effect through a stratified analysis of the data from the database research partners. Mantel-Haenszel methods will be used to summarize effects across strata. Crude and adjusted incidence rate ratios for each study endpoint and exposure category will be estimated comparing users of tacrolimus and users of pimecrolimus with users of corticosteroids. A secondary analysis will compare users of corticosteroids with untreated patients. Sensitivity analyses will be conducted to evaluate protopathic and surveillance bias. Separate analyses will be conducted for the pediatric and adult populations.

Milestones:

The study protocol version 4.0 dated April 10, 2013, was approved by the EMA.

The study was registered in the EU PAS Register in July 30, 2013 (<http://www.encepp.eu/encepp/viewResource.htm?id=4358>).

Phase I of the study was completed November 30, 2015. The study report was submitted to the EMA on December 11, 2015.

The JOELLE Extension involves the inclusion of 4 years of additional data. Depending on data availability, the extension may be longer in some of the study databases. The start of data collection is planned between Q3 2017 and Q1 2018. The final study report is expected to be completed in Q3 2019.

5 Amendments and Updates

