9.2.1 Study Period

[figure not shown]
The study Phase I covered the period from the date of first availability of topical tacrolimus and topical pimecrolimus in each study population through December 31, 2011. In the JOELLE Extension, the study period is extended for 4 years, with a period of inclusion of new users from the date of first availability of topical tacrolimus and topical pimecrolimus in each study population to December 31, 2014, and a follow-up of all new users through December 31, 2015. This ensures a follow-up of at least 6 months of all new users after applying a 6-month induction period. In some databases data beyond 2015 may be available and will be included in the study. In these databases, the study period will cover a period from the date of first availability of topical tacrolimus and topical pimecrolimus in each study population to 12 months before the end of data availability, and a follow-up of all new users up to the last date of data availability. Figure 1 shows the study period for Phase I and the JOELLE Extension for two scenarios of data availability: through December 31, 2015, and through December 31, 2016.

Figure 1. Study Period According to Two Scenarios of Data Availability

Data available through 31 December 2015

Data available through 31 December 2016

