In the CPRD, for practices linked to the cancer registry, cases will be identified using ICD-10 codes. For practices not linked to the cancer registry, cases will be identified through the CPRD records and linkage to Hospital Episode Statistics (HES) data. The linkage of CPRD data to cancer registry data will be performed in the study. Note that the linkage is partial, and there is a lag of 2 years for obtaining data from the cancer registry. Cases from linked practices for which cancer registry information is not available will be identified through CPRD records and HES, as for practices not linked to the cancer registry. The ICD-O-3 coding system is not used for coding neoplasms in the CPRD. Therefore, the standard reference medical terminology or diagnostic coding systems used in the database (Read/OXMIS) will be mapped to the ICD-O-3 topography and morphology codes for each endpoint. CTCLs will be identified using the selected ICD-O-3 codes that matched the definition and codes of cutaneous lymphomas in the WHO 2008 classification of lymphomas as described in Section 9.3.5. For cases identified

through the CPRD or the Hospital Episodes Statistics linkage, validation of all pediatric cases, a random sample of adult cases of melanoma skin cancers and lymphomas (number of cases to be determined based on the final number of cases identified), and all cases of non-melanoma skin cancer and CTCL will be performed by reviewing the computerized information.

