9.7.2 Pooled Analysis

The coordinating center will conduct an analysis of the propensity score-stratified data from each individual database and an overall analysis combining the data across all database research partners. For the JOELLE Extension, because data from Denmark cannot be shared outside the country, data from each data source will be centralized on the servers of Statistics Denmark through the University of Southern Denmark, and the coordinating center will conduct the pooled analysis remotely within these servers. The overall analysis will be designed to estimate the effect of the exposure while controlling for confounding using the data stratified on propensity scores. Mantel-Haenszel methods will be used to summarize effects across strata. Data source will be retained as a stratification variable, and the effect within each data source will be estimated. If some strata have zero cases, it may be possible to collapse neighboring propensity score strata within sites without introducing confounding, yielding fewer than 10 strata per site in the final stratified analysis. Before the final analysis, the amount of confounding reintroduced by collapsing of neighboring strata will be evaluated.

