The study will combine results from different databases with heterogeneity between databases regarding exposure information (prescribed vs. dispensed medications) and ascertainment of risk factors and confounders. Three of the study databases (PHARMO, Denmark, Sweden) are based on diagnoses when discharged from the hospital or in connection with a hospital outpatient clinic visit, whereas the CPRD is based on information from GPs (in Sweden, data from primary care have also recently become available). Ascertainment of covariates using hospital discharge diagnoses might result in the identification of individuals with more severe comorbidity. The effect of each database will be adjusted for in the overall stratified analysis.

Non-melanoma skin cancer is most probably underreported in cancer registries because reporting is not required or reporting has been required only in recent years. Although underreporting will result in underestimation of incidence rates, it is expected to have a nondifferential effect between users of tacrolimus and pimecrolimus and users of corticosteroids.

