Annex 3.

Summary of Characteristics of Databases

Table A3-1. Protopic and Malignancies: Main Features of Databases and Data Availability

Characteristic	CPRD, UK	PHARMO Netherlands	Danish Health Databases	Swedish National Registers
Database population in 2015 (million)	4.4	4.0	5.7	9.7
Database type	Primary health care electronic medical record database plus linkage to hospital data (Hospital Episodes Statistics [HES]) and cancer registry data	PHARMO Database Network holds several databases, linked on patient level. For this study, outpatient pharmacy data (dispensed drugs), hospitalization data, GP data, pathology data (PALGA), and Netherlands Cancer Registry (JOELLE Extension) data will be used.	Prescription registry (all reimbursed drugs dispensed by prescription since 1995) Danish National Registry of Patients (hospital admissions, outpatient visits, and emergency department visits) Cancer registry	Prescribed Drug Register (all drugs dispensed by prescription since July 1, 2005) Patient registers (hospital admissions and outpatient visits) and primary care database Cancer Register Register of the Total Population
Tacrolimus reimbursement approval	April 2002	November 2002	June 2002 Change in December 2008 (can be prescribed by MDs other than dermatologists)	June 2002
Study data: phase 1 availability timelines	2011 Data: CPRD: 1Q 2012 (data updated every 3-4 months; lag time 6-12 weeks) CPRD-HES: 3Q 2012 CPRD-cancer data: 2014	2011 Data: 3Q 2012 Hospital data: yearly available (7 months lag time) Complete database update: annually Q3, includes hospitalization data available up to previous year December (7 months lag time) Pharmacy, GP, PALGA available up to Q3	2011 Data: Mid 2012 Prescription data: annually available at midyear (lag time 6-18 months)	2011 data: Rx data: 3Q 2012 Cancer data: 1Q 2013 Prescription data (since July 1, 2005): 1 month lag time Cancer Register: 1 year lag time Patient Register: Up to 8 months lag time

Characteristic	CPRD, UK	PHARMO Netherlands	Danish Health Databases	Swedish National Registers

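### In linked CPRD practices the case source changes when registry cover ends, and the Mantel-Haenszel strata do not separate the two periods, so CPRD rate ratios for higher dose categories can be biased

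*Protocol*

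**What the plan says.** Section 9.3.6 identifies cases by ICD-10 code from the cancer registry in linked CPRD practices, and from CPRD records and HES in unlinked ones. It adds that "the linkage is partial, and there is a lag of 2 years for obtaining data from the cancer registry", and that "Cases from linked practices for which cancer registry information is not available will be identified through CPRD records and HES". The source can therefore change within one practice during follow-up. Registry cases need no validation. For cases found in CPRD or HES, computerized review is planned for all pediatric, NMSC and CTCL cases and for a sample of adult melanoma and lymphoma.

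Section 9.7.2 states: "Data source will be retained as a stratification variable, and the effect within each data source will be estimated". Section 9.7.2.3 lists the strata as propensity score deciles, age, sex and database partner. Case source, linkage status and calendar time of follow-up are not among them, and none of the nine sensitivity analyses in Section 9.7.2.5 addresses case source.

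Under Section 9.3.4.4, time at risk in a dose category starts 6 months after its cut-off is reached. Under Section 9.3.4.6, corticosteroid person-time runs from cohort entry and is not divided. Follow-up goes to 31 December 2015, but where later data exist Section 9.2.1 provides "a follow-up of all new users up to the last date of data availability".

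**The concern.** Cumulative dose is the main exposure. A patient reaches a high-dose category only some years after entry, so that person-time is late in calendar terms. If the registry stops before follow-up ends, a larger share of high-dose time than of comparator time has its cases found through GP records and HES. The CPRD rate ratio for that category then partly compares one case-finding system with the other.

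The propensity score includes calendar year of start date and practice or region (Annex 5). These balance when and where people enter. They do not balance how much of a category's person-time falls after a cut-off within the same practice. A difference in completeness between the two sources could create a dose trend in the CPRD results or hide one.

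**Working it through.** **1. Check on the follow-up distribution.** With bin midpoints, the 103,175 adults in Table 6 give 602,953.5 person-years. Removing 0.5 year each (51,587.5) leaves 551,366, against 551,369 in Table 3. The midpoints therefore reproduce the plan's own adult figure.

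**2. Length of the gap.** Gap = end of follow-up minus (extraction date minus lag). The Abstract says "The start of data collection is planned between Q3 2017 and Q1 2018".
- 2-year lag, follow-up to end 2015: extraction in Q3 2017 gives registry cover to July–September 2015, a gap of about 3 to 6 months. Extraction in Q1 2018 gives no gap.
- 3-year lag: about 0.75 to 1.5 years. Annex 3 makes this possible, since for 2011 data it lists "CPRD-cancer data: 2014", which is 2 to 3 years after the end of 2011.
- CPRD followed up to extraction: the gap equals the lag, 2 years or more.

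**3. Share of adult person-time in the gap.** For a gap of g years, share = Σ n·min(g, T − a) / Σ n·(T − a) over users with T > a. Here T is the Table 6 midpoint and a the start of the person-time. The comparator stand-in has a = 0. A cut-off reached at 2, 4 or 6 years has a = 2.5, 4.5 or 6.5. Example, g = 0.5: comparator 51,587.5 / 602,953.5 = 8.6%; cut-off at 4 years 29,928 / 202,934 = 14.7%.

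**4. Bias factor in linked practices.** With s = cases found by GP/HES relative to the registry, factor = (1 − f1 + f1·s) / (1 − f0 + f0·s), where f1 and f0 are the shares for the dose category and the comparator. The documents give no value for s; 0.5 to 1.5 is assumed. Example, g = 0.5, cut-off at 4 years, s = 0.5: (1 − 0.147 × 0.5) / (1 − 0.086 × 0.5) = 0.968.

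| Gap | Comparator share | Share, cut-off at 2 / 4 / 6 y | Factor (s = 0.5 to 1.5) at 2 y | at 4 y | at 6 y |
|---|---|---|---|---|---|
| 0.5 y | 8.6% | 11.6 / 14.7 / 19.8% | 0.984–1.014 | 0.968–1.030 | 0.941–1.054 |
| 1 y | 17.0% | 23.1 / 29.5 / 39.7% | 0.967–1.028 | 0.932–1.057 | 0.876–1.104 |
| 2 y | 33.2% | 43.1 / 53.4 / 69.0% | 0.940–1.043 | 0.879–1.087 | 0.785–1.154 |

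The 2-year row keeps the Table 6 distribution. If one year is instead added to every follow-up (to end 2016), the comparator share is 29% against 39%, 48% and 60%. The 6-year factor is then (1 − 0.60 × 0.5) / (1 − 0.29 × 0.5) = 0.82 at s = 0.5, and 1.30 / 1.146 = 1.13 at s = 1.5.

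For ever use with its 6-month lag, the share at a 1-year gap is 18.5% against 17.0%, so that contrast hardly moves.

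**5. Dilution.** Section 9.7.2.1 implies that CPRD holds about 21% of adults (100 − 79). Section 9.4 says over half of CPRD is linked; 0.5 is used. Pooled weight = 0.21 × 0.5 = 0.105. For the 6-year cut-off the pooled factor is 0.994–1.006, 0.987–1.011 and 0.977–1.016 for gaps of 0.5, 1 and 2 years; for example 1 − 0.105 × (1 − 0.785) = 0.977. These shifts scale with the linked share.

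**6. Whether the CPRD estimate will be read.** Adult NMSC: 286.2 per 100,000 × 0.21 × 551,369 person-years ≈ 331 cases among tacrolimus users, if person-time is proportional to users. In children, any lymphoma gives 2.1 per 100,000 × 0.10 × 133,285 ≈ 0.3 cases, so the point matters only for adults.

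**The case against.** The strongest objection is that the base plan may have almost no gap. The stated lag and planned dates give 0 to 6 months, and the Phase I timeline was itself extended because registry data were late, which suggests the study waits for them. This stands, and it keeps the point small. It does not remove it: the lag may be nearer 3 years, and Section 9.2.1 commits to including later data where they exist.

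A reader might infer that UK registry cover ends in 2014. The 2014 date in Section 9.3.6 belongs to the Netherlands Cancer Registry; no UK end date is given.

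A reader might also infer that the protocol declares all ascertainment error nondifferential. Section 9.9 does say "it is expected to have a nondifferential effect between users of tacrolimus and pimecrolimus and users of corticosteroids", but only about NMSC underreporting in cancer registries. It does not mention the CPRD change of source, melanoma or lymphoma.

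Nor do the documents support a false upward NMSC trend in particular. Annex 3 lists NMSC underreporting for CPRD as a whole, so which source finds more is unknown. The planned review limits false positives in CPRD and HES cases but cannot recover missed ones.

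Section 9.7.2.1 plans an analysis without CPRD. It is free of the problem, but its purpose is type of prescriber, and it does not correct the CPRD estimates.

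Finally, Sections 9.1 and 9.7 leave detail to local adaptation and the SAP. Here, however, the protocol itself fixes both the source rule and the strata.

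**Conclusion.** The point holds as a limited one. As written, the plan lets the CPRD dose- and duration-category rate ratios, which it commits to estimating, mix two case-finding systems in proportions that differ between exposure groups. For categories reached at 2 to 4 years, the linked-practice bias is about 3% or less at a 6-month gap, and about 5% for a category reached at 6 years. At gaps of 1 to 2 years it reaches roughly 5 to 20%, with the largest values for the latest categories and the widest detection difference. The sign is unknown.

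These figures rest on assumed relative detection of 0.5 to 1.5, assumed times to reach the dose cut-offs (the protocol leaves the cut-offs open), and CPRD users and comparators having the four-country Table 6 follow-up pattern. The ever-use results and the pooled adult conclusions are not in question. This is a cheap improvement, not a defect that undermines the study.

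**What to change.** Record the date at which registry cover ends for linked CPRD practices. In Section 9.7.2, split CPRD person-time and events into registry-covered and not-covered time and treat these as separate data-source strata. Any collapsing of sparse propensity score strata should stay within them. If cells become too sparse, add to Section 9.7.2.5 a sensitivity analysis that censors linked practices at the registry end date. In Section 9.9, state that the nondifferential expectation for NMSC underreporting does not extend to the CPRD change of source.

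Rewording Section 9.3.6 to use GP records and HES throughout, with registry cases added where covered, would not be enough: the sources would still change at the cut-off.

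The split discards no person-time and costs somewhat sparser CPRD cells. Censoring costs 8.6%, 17.0% or 33.2% of linked-practice adult person-time for gaps of 0.5, 1 or 2 years. Multiplied by 0.105, that is about 0.9%, 1.8% or 3.5% of the pooled adult total, in that sensitivity analysis only.

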9.3.6.1 Assessment of Protopathic Bias for CTCL

Evaluation of potential protopathic bias for CTCL cases will be conducted in the CPRD and Sweden.

In the CPRD, pending ISAC approval, researchers will send questionnaires to general practitioners requesting additional information to assess protopathic bias. Information may include date of CTCL diagnosis; date of start of symptoms; reasons for prescribing topical tacrolimus, pimecrolimus, or corticosteroids; physician suspicion of CTCL before start of treatment; skin conditions before start of treatment (e.g., psoriasis); location and extent of CTCL; biopsy results; date of onset of symptoms of atopic dermatitis; location and extent of atopic dermatitis; and details of topical treatment (amount, frequency, duration).

Similarly, in the JOELLE Extension in Sweden, pending ethics approval, researchers will aim to review the medical records of cases of CTCL with the purpose of identifying information indicating whether CTCL symptoms were already present at the time of the start of the exposure.

9.3.7 Confounding and Risk Factors

A number of diseases and conditions have been associated with the risk of skin cancer and lymphoma. The main risk factors are age, sex, immunosuppressive disease and use of immunosuppressive agents, chronic disease, severe skin diseases, frailty and general health status, intensity of sun exposure, and skin phenotype [5,9,16]. Atopic dermatitis and severity of atopic dermatitis have been associated with an increased risk of skin cancer and lymphoma [8], which can lead to confounding by indication as tacrolimus, pimecrolimus, and corticosteroids are indicated for the treatment of atopic dermatitis.

We will use propensity scores and stratification by categories of propensity scores to control for confounding and confounding by indication, in particular. Ascertainment of confounders and risk factors will be based on the information available in each database. Estimation of propensity scores at the start date will include demographic variables, lifestyle habits, medical history, use of medications, and utilization of health care services. A detailed list of variables is presented in Annex 5.

In Phase I, to assess unmeasured confounding, researchers at PHARMO and the CPRD explored the feasibility of obtaining additional information on risk factors that are known to be of relevance but are not captured in databases (e.g., severity of atopic dermatitis, history of sun exposure, or treatment with ultraviolet A phototherapy [UVA]). The clinical review of patient profiles and free-text comments of a sample of users in PHARMO-GP and the CPRD did not provide any additional relevant information on unmeasured confounding factors.

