Disease and procedures dictionary codes	CPRD: Read HES: ICD-9-CM discharge diagnoses Cancer registry: ICD-10	Hospitalization: ICD-9-CM and ICD-10 discharge diagnoses PALGA: PALGA codes based on SNOMED ICD-O-3 coding Netherlands Cancer Registry: ICD-10	ICD-10	ICD-9 and ICD-10
Outpatient diagnoses	Yes	Yes (subset in GP database)	Yes (only at hospitals)	Yes (at hospitals and primary care setting)
Hospital diagnoses	Recorded by GPs and partial linkage to HES	Yes	Yes	Yes
Outpatient specialist care	Specialists referral letters	Yes for subset GP database with specialist referral letters	Yes (only at hospitals)	Yes (only at hospitals)
Medical history/ comorbidities	GP data and hospital diagnoses (partially through HES linkage)	Available as hospital discharge diagnoses for hospitalized patients. For a subset, available in GP database.	Hospital (inpatient and outpatient data)	Hospital (in- and outpatient data) and primary care data
Atopic dermatitis	Read codes, specialist-reported diagnosis, free text	Algorithm: based on hospital outpatient or inpatient diagnosis and medications	Algorithm: based on hospital outpatient or inpatient diagnosis and medications	Algorithm: based on primary care and hospital (outpatient or inpatient) diagnoses and medications
Atopic dermatitis severity	Algorithm: specifications pending	Algorithm: specifications pending	Algorithm: specifications pending	Algorithm: specifications pending

Characteristic	CPRD, UK	PHARMO Netherlands	Danish Health Databases	Swedish National Registers
Validation atopic dermatitis diagnosis	Review of patients records and physician's questionnaires.	Linkage to GP data (about 8% of patients) possible but very intensive effort	Outpatient diagnosis available at national level but not able to be validated	No link to patients available Record review for patients seen at hospitals possible but difficult for patients seen by GPs Review of free text in prescription register
Immunosuppressive diseases (HIV, AIDS)	Yes	Yes (pharmacy and hospitalizations data used as proxies)	Not available (confidential data)	Not available (confidential data)
Sun exposure (intensity), ultraviolet light therapy	Regional sun exposure estimates as proxy	Hospital codes for ultraviolet (UV) light therapy available but number treated is low (about 40 patients)	No	Information on ultraviolet light therapy is available (procedure codes in the patient register)

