Chronic disease	Malignancy (140-171, 174-199, 203-208, 230-231, 232-238.1, 238.3-238.9) excluding skin cancer (172,173, 232, 238.2) and lymphoma (200-202)
	Renal failure (584)
	Chronic liver disease and hepatic failure (570, 571, 572.2, 572.3, 572.4, 573)
	Ischemic heart disease (410-414)
	Hypertensive disease (401-405)
	Heart failure (428)
	Other cardiovascular diseases (390-398, 415-417, 420, 427,429, 440-448)
	Cerebrovascular diseases (430-438)
	Diabetes mellitus (250)
	Chronic obstructive pulmonary disease (COPD), emphysema, respiratory insufficiency (491, 492, 496, 518.8)
	Musculoskeletal system and connective disease (excluding rheumatoid arthritis, systemic lupus erythematosus, and Sjögren's syndrome) (710.1, 710.3-710.9, 711-713, 715-739)
	Organ transplantation (V42, V43.2, 996.8)
	HIV infection or AIDS (042, V08)

Use of Medications

At least one prescription recorded within 1 year before the start date (yes/no, unless other parameters are specified)

Medication Category	Individual Variables To Be Evaluated (ATC code)
Use of immunosuppressant, immunostimulant and cytostatic drugs	Systemic corticosteroids (H02AB, H02B)
	Systemic tacrolimus (L04AD02)
	Azathioprine (L04AX01)
	Methotrexate (L01BA01, L04AX03)
	Ciclosporin (L04AD01)
	Other antineoplastic agents excluding methotrexate (L01 except L01BA01)
	Other immunosuppressants (L04AA, L04AB, L04AC, L04AD03, L04AX02, L04AX04, L04AX05, L04AX06)
	Immunostimulants (L03)
Antipsoriatics for topical use	Systemic antivirals (J05)
	Tars (D05AA)
	Antracene derivatives (D05AC) (dithranol and dithranol combinations)
	Psoralens for topical use (D05AD) (trioxsalen, methoxsalen)
Antipsoriatics for systemic use	Other antipsoriatics for topical use (D05AX) (fumaric acid, calcipotriol, calcitriol, tacalcitol, tazarotene, calcipotriol combinations)
	Psoralens for systemic use (D05BA) (trioxsalen, methoxsalen, bergapten)
	Retinoids (D05BB) (etretinate, acitretin)
Other dermatological preparations excluding topical corticosteroids	Other antipsoriatics (D05BX) (fumaric acid derivatives, combinations)
	Topical salicylic acid preparations (D02AF, D01AE12)
Other drugs	Other dermatological agents (D01-D04, D06, D08-D11)
	Cardiovascular system drugs (excluding lipid-modifying agents) (C01-C09)
	Anti-inflammatory and antirheumatic agents, nonsteroidal (M01A)
	Other antirheumatic agents (M01B, M01C)
	Hormone-replacement therapy (G03C, G03E, G03F)
	Lipid-modifying agents (C10)
	Insulins (A10A)
	Oral antidiabetics (A10B)

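### Annex 3 says ultraviolet light therapy is recorded in Sweden, but Section 9.3.7 lists it as not captured and Annex 5 gives it no covariate

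*Protocol*

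**What the plan says.** Section 9.3.7 sets a general rule: "Ascertainment of confounders and risk factors will be based on the information available in each database". It then reports a Phase I exercise on unmeasured confounding, in which "researchers at PHARMO and the CPRD explored the feasibility of obtaining additional information on risk factors". The factors in question are described as relevant ones that "are not captured in databases (e.g., severity of atopic dermatitis, history of sun exposure, or treatment with ultraviolet A phototherapy [UVA". The exercise found nothing useful. Sweden was not part of it.

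The row of Annex 3, Table A3-1, on sun exposure and ultraviolet light therapy gives a different picture for each database:

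- Sweden: "Information on ultraviolet light therapy is available (procedure codes in the patient register".
- PHARMO: "Hospital codes for ultraviolet (UV) light therapy available but number treated is low (about 40 patients".
- CPRD: "Regional sun exposure estimates as proxy", with no therapy record mentioned.
- Denmark: a plain no.

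Annex 5, the covariate list to which Section 9.7.1.4 refers, contains no ultraviolet-therapy or phototherapy item. The nearest entries are topical psoralens and "Psoralens for systemic use (D05BA) (trioxsalen, methoxsalen, bergapten", both counted only if prescribed in the year before the start date. None of the nine sensitivity analyses in Section 9.7.2.5 deals with ultraviolet therapy.

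**The concern.** The protocol itself calls this treatment a relevant risk factor, and skin cancer is part of the primary objective. Its own data-source table says that one of the four databases records the treatment, yet the covariate list does not use it. Database-specific covariates are already normal in Annex 5: smoking and body mass index are marked for the CPRD, socioeconomic status for PHARMO and the CPRD, and prescriber type for PHARMO, Denmark and Sweden. A Sweden-only variable would fit that pattern.

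Unequal prior use between cohorts is plausible. Section 7.2 and Table 2 describe tacrolimus as intended for moderate to severe disease that has not responded to conventional treatment. A comparator patient needs only a recorded diagnosis plus one corticosteroid prescription, or two prescriptions within 12 months (Section 9.2.3). If phototherapy use differs between the cohorts and affects skin-cancer risk, the Swedish rate ratios, and through them the pooled ones, would carry a bias that could have been measured.

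**Working it through.** The protocol states no figure on this point, so there is nothing to reproduce. The main check is textual; the arithmetic only sets a scale.

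**1. Passages side by side.** Section 9.3.7 uses the general word databases, but its sentence concerns PHARMO and the CPRD. For the CPRD it agrees with Annex 3. For PHARMO it is nearly right, because codes exist but cover about 40 patients. For Sweden, Annex 3 states that the information is available. Section 9.3.7 names ultraviolet A specifically, while Annex 3 speaks of ultraviolet light therapy in general, so a Swedish variable would cover the wider category. Whatever the scope of the Section 9.3.7 sentence, the Swedish gap in Annex 5 remains, and it does not sit with the rule on using what each database holds.

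**2. Swedish share of source population** (Annex 3, millions): 9.7 / (4.4 + 4.0 + 5.7 + 9.7) = 9.7 / 23.8 = 0.41. This is a share of population, not of tacrolimus users or person-years. Swedish prescription data start only in July 2005.

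**3. Pooled precision in adults.** Inputs are 551,369 tacrolimus person-years (Table 3), the Table 4 rates, and a comparator ratio of up to 4:1 (Section 9.7.1.4). With a exposed events, SE(log RR) = sqrt(1/a + 1/(4a)) and the 95% factor is exp(1.96 × SE), assuming a rate ratio of 1 and no stratification.

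- Non-melanoma: a = 286.2/100,000 × 551,369 = 1,578; SE = 0.0281; factor 1.06 (1.07 at 1:1).
- Melanoma: a = 34.7/100,000 × 551,369 = 191; SE = 0.0808; factor 1.17.

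**4. Scale of a possible bias.** For one binary confounder, the factor is [1 + p1(R − 1)] / [1 + p0(R − 1)]. Here p1 and p0 are the treated proportions in tacrolimus and corticosteroid users, and R is the relative risk for skin cancer. All three are assumptions.

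| R | p1 | p0 | Factor |
|---|---|---|---|
| any | 5% | 5% | 1.00 |
| 1.5 | 5% | 2% | 1.025/1.010 = 1.01 |
| 2 | 10% | 5% | 1.10/1.05 = 1.05 |
| 3 | 10% | 5% | 1.20/1.10 = 1.09 |
| 5 | 15% | 5% | 1.60/1.20 = 1.33 |
| 2 | 5% | 10% | 1.05/1.10 = 0.95 |

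**5. What a Swedish covariate can reach.** The factors in step 4 apply only where the assumed prevalences hold. If Sweden carried 41% of the pooled weight (an assumption taken from step 2), full adjustment there would move the pooled estimate by 1.05^0.41 = 1.02 to 1.09^0.41 = 1.04 in the two middle cases.

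**6. PHARMO.** Suppose all 40 patients were adult tacrolimus users, out of 98,788 in Table 3, and no corticosteroid user was treated. The factor is then 1 + (40/98,788)(R − 1), which is 1.0004 at R = 2 and 1.0036 at R = 10. This is negligible.

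**The case against.** Four arguments weigh against the point.

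- *The sentence in Section 9.3.7 is Phase I history about two databases.* This stands. A reader might infer that the protocol declares ultraviolet therapy unavailable across the whole study, and the text does not go that far. The loose wording still needs correcting, and the Swedish omission from Annex 5 does not depend on it.
- *The high-dimensional algorithm, or the code lists left to the statistical analysis plan, may bring the variable in.* Section 9.7.1.4 introduces Annex 5 as the covariates to be evaluated and then describes selection. It does not say that selection goes beyond that list. Annex 5 ascertains clinical history through diagnoses, prescriptions and visits, with no procedure codes. The plan was not available for this review, so non-adjustment is possible rather than proven.
- *Proxies cover it.* This stands in part. Annex 5 lists psoralens, psoriasis, antipsoriatics, other inflammatory skin disease, a severity flag and dermatologist visits, and results are stratified by prescriber type in Sweden. However, psoralens have a one-year window, and Section 9.7.2.5 says the health-care-use information behind the Phase I severity definition was only partially available.
- *Size and direction are unknown.* This stands. A reader might infer that the adult skin-cancer rate ratio is confounded upward. The documents do not support that, since they give no prevalence by cohort and no effect on skin cancer. Section 7.1 notes that dermatologists may avoid these drugs in patients at high risk of skin cancer. Section 9.3.1 dropped the psoriasis-related exclusions for all cohorts, so patients treated with ultraviolet light may sit in either arm.

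**Conclusion.** The point holds as an internal inconsistency and an avoidable gap. Annex 3 says Sweden records ultraviolet light therapy, Section 9.3.7 lists ultraviolet A treatment among uncaptured factors, and Annex 5 has no such covariate. A recorded potential confounder of the skin-cancer endpoints may be left unadjusted in the database with the largest source population.

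The residual bias after the proxies could be nil or could go either way. The illustrative factors of 1.05 to 1.09 are near or above the pooled adult non-melanoma confidence factor of 1.06, which makes the variable worth checking, but they rest wholly on assumed prevalences and relative risks. It would also be wrong to read them as the pooled bias that the fix would remove. A Swedish variable acts only in Sweden, PHARMO's roughly 40 patients do not matter, and Annex 3 lists no ultraviolet-therapy record for Denmark or the CPRD. The change should be made because it is cheap and concerns a primary outcome, not because bias has been shown.

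**What to change.** 1. Correct Section 9.3.7 to say that ultraviolet therapy is recorded in Sweden through patient-register procedure codes, and limit the statement about uncaptured factors to the databases it describes.
2. Add to Annex 5, as a propensity-score covariate and cohort descriptor: *Ultraviolet light therapy (procedure codes) at any time before the start date: yes/no (Sweden)*.
3. Add to Section 9.7.2.5 a sensitivity analysis reporting the Swedish adult skin-cancer rate ratios with and without this covariate.

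No PHARMO variable is needed. The Swedish shift need not be carried over to other countries as a bias parameter, though it may inform the discussion of residual bias in Denmark and the CPRD. If the Swedish codes turn out to be unusable, the protocol should say so and why.

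The cost is a little extra programming on a register already in the study, plus the protocol wording. The limitation is that register codes may miss phototherapy given outside hospital-based care.
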